### **VIII. Data Management and Analyses**

All hard copies of the data will be kept in a folder, in a locked file cabinet in a locked office in a secure building. Data will be double-entered into appropriate data management software, correcting all data entry errors prior to import into SAS (v 9.2) for statistical analyses.

Standardized descriptive statistics including means, median, standard deviations, frequency and ranges for continuous variables will be calculated to describe the participants and the overall and subscale means for the respective instruments. For specific aim 1, the number of participants who achieve sufficient levels of serum 25(OH)D will be calculated, and paired t tests will be used to assess differences between mean laboratory values from baseline and follow up. Using logistic regression, we will also explore the clinical characteristics of those who achieve sufficient levels vs. those who remain insufficient after the intervention. For specific aim 2, repeated measures analyses will be conducted to examine changes in symptom scales from baseline to interim and follow up.

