## I. Abstract:

**Background:** Several clinical trials are underway to investigate if variable forms of vitamin D (D2 vs. D3) prescribed at different doses (10,000-50,000 IUs/week) can improve the side-effects associated with treatment for estrogen receptor positive (ER+) breast cancer, specifically aromatase inhibitors (AIs.) Presumably for generalizability and potential safety purposes, these trials predominantly exclude women with metastatic breast cancer (MBC); a rapidly expanding sector of the cancer survivor population who experience significant treatment-related side-effects. Evaluation of the safety of vitamin D3 supplementation is crucial since supplementation can lead to hypercalcemia and importantly, *in vitro* studies have shown that vitamin D3 influences the transcription of a gene that increases estrogen production. To assure that vitamin D3 does not abrogate the clinical effects of anti-estrogen therapies, the effect of vitamin D3 supplements on estrogen production requires an evaluation that further explores and defines its potential role in symptom management for this population.

**Objectives:** This pilot study will evaluate the feasibility of vitamin D3 supplementation (n=25) in women with MBC, providing much needed data on the preliminary safety and efficacy of this treatment in this patient population. This study will determine: 1) if weekly supplementation of high dose vitamin D3 increases serum levels of 25(OH)D without adverse effects *related* to such therapy (primary aim); 2) the effects of vitamin D3 supplementation on symptom management (secondary aim); and 3) if vitamin D3 supplementation is associated with improved biomarkers of inflammation (exploratory aim.) Additionally, we will examine the prevalence of symptoms and quality of life in (n=25) women with advanced breast cancer who have normal serum levels to investigate associations with biomarkers of inflammation.

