### III. Study Aims

Several clinical trials are underway to investigate if vitamin D2 or D3 provided at various doses (10,000-50,000 IUs/week) can improve the side-effects associated with anti-estrogen therapies, specifically aromatase inhibitors (AIs). However, these current trials use variable forms of vitamin D and predominantly include women with Stage I-III disease, excluding women with metastatic breast cancer. Evaluation of the safety of vitamin D3 supplementation is crucial since supplementation can lead to hypercalcemia and importantly, *in vitro* studies have shown that vitamin D3 influences the transcription of a gene that increases estrogen production. To assure that vitamin D3 does not abrogate the clinical effects of anti-estrogen therapies, the effect of vitamin D3 supplementation on estrogen production requires evaluation. Therefore, the overarching goal of this pilot study is to evaluate the safety, feasibility and efficacy of vitamin D3 supplementation in women with MBC. We will address and test the following aims and hypotheses, respectively:

**Aim 1:** To determine if weekly supplementation of 50,000 IUs of vitamin D3 raises serum levels of 25(OH)D to >30 mg/dl without adverse effects.

**Hypothesis 1:** Women who are compliant with vitamin D3 supplementation, as evidenced by normalization (>30 mg/dl) or increases in their serum 25(OH)D levels, will not experience significant changes in serum calcium or serum estradiol levels.

**Aim 2:** To determine the effect of vitamin D3 supplementation on symptom management.

**Hypothesis 2:** Women who achieve serum concentrations of 25 (OH)D ≥30 mg/dl or experience significant increases in 25(OH)D will exhibit improvements in pain, fatigue, sleep, mood, muscle function and overall quality of life.

**Exploratory Aim:** To explore the mechanistic effects of serum vitamin D levels and vitamin D3 supplementation on inflammatory markers and potential associations with symptom management.

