**d. Study endpoints:** The primary endpoint in this study is serum 25(OH)D. We will use this serum biomarker to assess if repletion levels are obtained ( $\geq 30$  ng/dl), to test associations with symptoms and/or to assess the degree of change from baseline to follow up. Serum calcium and serum estradiol levels will be monitored to be sure these levels normalize or to assess clinically significant changes following supplementation, respectively.

To address our secondary endpoints, we will be assessing symptoms, including pain (Brief Pain Inventory; Cleeland, 1994; FACT-Bone pain, Broom, 2009), fatigue (Piper Fatigue Scale; Piper, 1998), mood (Hospital Anxiety and Depression Scale; Herrmann, 1997; Patient Health Questionnaire-8; Kroenke, 2001), muscle function (handgrip strength), sleep (Pittsburg Quality Sleep Index; Carpenter, 1998), overall health and QOL (FACT-B; Brady, 1997; FACT-ES; Fallowfield, 1999.) These specific tools were selected because they have been utilized in breast cancer populations and/or other cancer populations and will provide the ability to compare our findings to others. In addition, to address important confounders, we will gather data on diet (Block Calcium/Vitamin D screener; Cummings, 1987), physical activity (Godin Leisure Time Activity, 1985), body composition (bioelectrical impedance, dual energy x-ray

absorptiometry), sunlight exposure (Glanz sunlight exposure, 2008), social support (Multiple Outcomes Social Support; Sherbourne, 1991) and previous/current breast cancer treatments.

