Protocol title: Safety, feasibility and efficacy of vitamin D supplementation in women with metastatic breast cancer (SAFE-D)

NCT: 02186015

Date: November 14, 2018

Protocol title: Safety, feasibility and efficacy of vitamin D supplementation in women with metastatic breast cancer (SAFE-D)

Principal Investigator: [name], RD

Research Team: [name], MS; [name], [name], RN; [name]; [name];

Statistical Analyses Conducted

Descriptive statistics were conducted to examine differences in sociodemographics, medical characteristics and dietary intake stratified by sufficient vs. insufficient serum 25(OH)D at baseline. Statistical differences between groups were assessed with Wilcoxon rank sum tests for continuous variables and chi-square or Fisher's exact test for nominal variables. Among those treated with 8 weeks of high dose cholecalciferol, changes from baseline were assessed with Wilcoxon signed rank tests for continuous scores. Analyses were performed with SAS version 9.4 (Cary, NC). A p value of <0.05 was used to denote statistical significance and based on the exploratory nature of this study, a p value of <0.10 was used to designate statistical trends.

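### Aim 1 asks for repletion without adverse effects, but its analysis counts repletion and tests average laboratory change, which is insensitive to harm in individual women

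*Protocol*

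**What the plan says.** Protocol Section III states Aim 1 as whether weekly supplementation "raises serum levels of 25(OH)D to >30 mg/dl without adverse effects". The Objectives in the Abstract give the same aim with attribution added: "without adverse effects *related* to such therapy (primary aim". Hypothesis 1 expresses the safety part through laboratory values: women whose 25(OH)D normalizes or rises "will not experience significant changes in serum calcium or serum estradiol levels".

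Section V.d is narrower: "The primary endpoint in this study is serum 25(OH)D". Calcium and estradiol are monitored alongside it, in part "to assess clinically significant changes following supplementation, respectively".

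For Aim 1, Section VIII states that "the number of participants who achieve sufficient levels of serum 25(OH)D will be calculated, and paired t tests will be used" to compare mean laboratory values at baseline and follow-up, and it adds an exploratory logistic regression on sufficiency. In the SAP, among treated women, "changes from baseline were assessed with Wilcoxon signed rank tests for continuous scores". Neither place lists a table of adverse events, a count of women beyond a laboratory limit, or a count of women replete without harm.

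Section VII works woman by woman. Every treated woman is evaluable for toxicity under CTCAE 4.0. There are individual limits for calcium (10.5 and 11.5 mg/dL) and for 25(OH)D, and an off-study criterion for estradiol that has no number. All safety measurements are reviewed after 7, 19 and 25 patients to decide whether the study continues.

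**The concern.** Hypercalcaemia, intolerance and a marked estradiol rise happen to individual women. A mean or median shift over 20 to 25 women barely registers one, two or three of them. Followed as written, the Aim 1 analysis could report most women replete and calcium not significantly changed while several had a related toxicity. Hypothesis 1 would then appear supported by a test with little chance of contradicting it.

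Two procedures add to this. A woman whose supplement is suspended still has her follow-up blood taken eight weeks after starting, when a raised value may already have fallen. The extra blood draw at discontinuation for toxicity has no place in a baseline-to-follow-up comparison. At stake is whether a trial with safety in its title answers the safety half of its primary aim.

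**Working it through.** **Inputs from the documents.** Intervention arm 25 and attrition about 20% (Protocol V.c); significance at p < 0.05 and trend at p < 0.10 (SAP). Two-sided testing is assumed, since sidedness is not stated.

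**The plan's own figure.** 25 × (1 − 0.20) = 20 completers, as stated. There is no power figure to reproduce.

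**Paired t test when k of n women rise by the same amount d and the rest do not change.**
- Mean change = kd/n.
- Variance of change = d² × k(n − k) / [n(n − 1)].
- t = mean / (SD/√n) = √[k(n − 1)/(n − k)].

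The size of the rise, d, cancels: a larger rise inflates the SD in proportion.

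| k | n = 20: t, p | n = 25: t, p |
|---|---|---|
| 1 | 1.00, 0.33 | 1.00, 0.33 |
| 2 | √(2×19/18) = 1.45, 0.16 | √(2×24/23) = 1.45, 0.16 |
| 3 | √(3×19/17) = 1.83, 0.083 | √(3×24/22) = 1.81, 0.083 |
| 4 | √(4×19/16) = 2.18, 0.042 | √(4×24/21) = 2.14, 0.043 |

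The critical values are 2.093 and 2.064, so significance first appears with the fourth woman. Three affected women are 15% of 20 or 12% of 25. Three would fall under the SAP's trend label; one or two would not.

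**With random variation, and with the SAP's test.** Simulation assumed a calcium rise of 2.1 mg/dL in affected women (for example 9.5 to 11.6) and a normal change with mean 0 and SD 0.2 to 0.5 mg/dL in the others, for n = 20 and n = 25. None of these values is in the documents.
- Two affected: non-significant in 92–98% of trials (paired t) and about 92–93% (signed rank).
- Three affected: non-significant in 81–87% (paired t) and 86–90% (signed rank).

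With two affected, the chance of significance is not far from the 5% false-positive rate. Moving from the t test to the signed-rank test does not cure the problem.

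**A non-significant result is not evidence of no change.** At 80% power the smallest detectable mean change is 0.66 SD (n = 20) or 0.58 SD (n = 25).

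**What counts per woman would show.** Exact (Clopper-Pearson) 95% intervals out of 25 treated:
- 0 events: 0–13.7%
- 1 event: 0.1–20.4%
- 2 events: 1.0–26.0%
- 3 events: 2.5–31.2%

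A true harm rate of 10% would show at least one case with probability 1 − 0.9²⁰ = 0.88 (n = 20) or 1 − 0.9²⁵ = 0.93 (n = 25).

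**Repletion alone against repletion without a related event.** Assume 18 women replete, 4 of them with a related event.

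| Denominator | Replete | Replete, no related event |
|---|---|---|
| 20 completers | 18/20 = 90% (68.3–98.8) | 14/20 = 70% (45.7–88.1) |
| 25 treated, non-completers as failures | 18/25 = 72% (50.6–87.9) | 14/25 = 56% (34.9–75.6) |

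The comparison must stay within a row. Going from 90% to 56% would mix the joint definition with a change of denominator, which accounts for 18 of the 34 points.

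**The case against.** The strongest reply is that the study does assess individual harm. Section VII grades and attributes toxicity in every treated woman and requires a full review at 25 patients, the whole intervention arm. This stands. A reader might infer that individual harms go unmonitored, and the documents do not support that. But Section VII states the purpose of the reviews as continuing or terminating the study, and nothing carries their findings into the Aim 1 result.

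Second, a joint outcome in the same woman is the natural reading of Aim 1 and Hypothesis 1, but no section writes it as a composite endpoint, and Section V.d names 25(OH)D alone. This also stands. The plan does not contradict a defined composite; its endpoint and analysis are narrower than its aim. The SAP describes analyses in the past tense, so a joint proportion belongs there as an added summary, not a new headline endpoint.

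Third, this is a pilot without power claims. True, but Section V.c gives estimates and interval widths as its purpose, and counts with exact intervals serve that directly.

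Two further inferences are tempting and fail. Section V.d says "Serum calcium and serum estradiol levels will be monitored to be sure these levels normalize", and since entry requires calcium of at most 10.4 mg/dl, it may seem that nothing could need normalizing. But entry sets only an upper limit, so low values are allowed. It may also seem that Aim 1 without attribution is unattainable, because 92% of women in the earlier pilot reported pain and 60% fatigue. Those are symptom prevalences from a questionnaire study, not adverse events, and both the Abstract and the toxicity rules in Section VII use attribution.

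**Conclusion.** The concern holds for the analysis and reporting of Aim 1, not for surveillance. The stated tests can return no significant change with up to three affected women out of 20 or 25, in both the protocol's and the SAP's form. The closed-form result needs no assumed SD or size of rise, only equal rises, no change in the other women and two-sided testing. The simulated percentages and the repletion counts rest on assumed values and are illustrations. Severity: should fix.

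**What to change.** For Aim 1, report the following among all women who took at least one dose, with exact 95% confidence intervals:

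1. The number with a supplement-related CTCAE event, using the Abstract's attribution wording throughout, with all events also listed by grade whatever their attribution.
2. The number with any observed value, scheduled or unscheduled, beyond each calcium and 25(OH)D limit already in Section VII, and the number meeting the estradiol criterion, which the investigators must define numerically. Routine laboratory values are planned only at baseline and week 8, so the table should say that these are observed crossings.
3. As an added summary, the proportion replete at week 8 with no related adverse event, for completers and for all treated women with non-completers counted as failures, beside the repletion-only proportion on the same denominators.

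Keep the mean and signed-rank tests as description, and do not conclude safety from a non-significant result. Before counting, reconcile the 25(OH)D cut-off (above 30 in Aim 1; at or above 30 in Hypothesis 2 and Section V.d) and the units (mg/dl, ng/dl and ng/ml in different sections).

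The cost is some protocol and SAP wording, one definition from the investigators and one table, mostly from logs and laboratory values already collected. The proportion replete without a related event cannot exceed the repletion-only figure, so the summary may look less favourable.

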### **IX. Other considerations**

**a. Potential benefits of the proposed research and future directions:** Seeking to live as normal a life as possible, including the ability to fulfill roles and maintain relationships, is a goal for many that are negatively affected by MBC. Many patients with MBC have serious concerns, including the fear of dying, declining quality of life, side effects of treatment, the ability to care for family, decreasing physical functioning and care at the end of life. Managing symptoms to maintain an optimum quality of life is the major goal of care in the metastatic setting. Many women with MBC who consume vitamin D take it to 'protect their bones.' This study has the potential to provide preliminary evidence to support that vitamin D levels can improve QOL and enhance survivorship care. Additionally, we will be asking participants to biobank their blood for future studies related to vitamin D. Findings from this study will be used for to design and justify a larger trial.

**b. Timeline:** This study is designed and intended to be completed within 18 months. We anticipate that we can screen, recruit and enroll 25 women in the intervention in months 1-12. We will enroll women in the cross-sectional arm of this study until the intervention is complete. Data entry will be on-going throughout the study with final data collection will conclude in month 14. In month 15, we will complete data entry, conduct data cleaning and begin initial statistical analyses. In months 15-18, we will complete our statistical analyses and prepare these data for grant, manuscript and oral presentation.

**c.** This study completed an IND application and has been issued a "study may proceed" decision by the FDA.

## **VII. Appendices**

### **A. Study Instruments**

1. Demographics and treatments
2. Brief Pain Inventory- Short form
3. Piper Fatigue Scale
4. Hospital Anxiety and Depression Scale
5. Patient Health Questionnaire 8
6. Eastern Cooperative Oncology Group Performance Status
7. Pittsburg Sleep Quality Index
8. Functional Assessment of Cancer Therapy-Breast and Endocrine Symptoms
9. Sunlight Assessment
10. Block Calcium/Vitamin D screener
11. Godin Exercise Leisure-time Questionnaire
12. Medical Outcomes Study Social Support Survey
13. Food Sources of Calcium
14. FACT-Bone Pain
15. Fruit, vegetable and fiber screener

Protocol title: Safety, feasibility and efficacy of vitamin D supplementation in women with metastatic breast cancer (SAFE-D)

NCT: 02186015

Date: November 14, 2018

Protocol title: Safety, feasibility and efficacy of vitamin D supplementation in women with metastatic breast cancer (SAFE-D)

Principal Investigator: [name], RD

Research Team: [name], MS; [name], [name], RN; [name]; [name];

Statistical Analyses Conducted

Descriptive statistics were conducted to examine differences in sociodemographics, medical characteristics and dietary intake stratified by sufficient vs. insufficient serum 25(OH)D at baseline. Statistical differences between groups were assessed with Wilcoxon rank sum tests for continuous variables and chi-square or Fisher's exact test for nominal variables. Among those treated with 8 weeks of high dose cholecalciferol, changes from baseline were assessed with Wilcoxon signed rank tests for continuous scores. Analyses were performed with SAS version 9.4 (Cary, NC). A p value of <0.05 was used to denote statistical significance and based on the exploratory nature of this study, a p value of <0.10 was used to designate statistical trends.
